### **8.3. General Considerations**

Continuous variables will be summarized by the standard descriptive statistics: number of patients (n), mean, standard deviation, median, minimum, and maximum for baseline variables, and n, mean, standard error, and confidence interval (CI) for outcome measures. Frequency of patient or events and percentages will be summarized for categorical variables. Time to event variables will be summarized using Kaplan-Meier methods.

Unless otherwise specified, all regression models will be stratified by maximum symptom severity at baseline (presence vs absence of moderate or severe symptoms) and by age ( $\leq 65$  years vs  $> 65$  years), and Wald p-values will be considered primary.

The statistical analysis plan will be finalized prior to unblinding and it will include a more technical and detailed description of the statistical analyses.

### **8.4. Efficacy Analysis**

The analysis of treatment efficacy will be based on the Intent-to-Treat Population. The PP population will be used for secondary analysis. This section is a summary of the planned efficacy analyses of the most important efficacy endpoints including primary and key secondary efficacy endpoints.

#### **8.4.1. Analysis of Primary Endpoints**

The primary analysis will be conducted when all patients have either withdrawn from the study, died, or been followed for at least 28 days ( $\pm 2$  days) since first dose on Day 1.

##### **8.4.1.1. Time to Sustained Clinical Resolution**

The primary endpoint is time to sustained clinical resolution as determined by symptom score. Sustained clinical resolution is defined in Section 7.1.1. The primary analysis of this endpoint will be performed on the ITT population. Time to sustained clinical resolution will be summarized by treatment group using Kaplan-Meier methods. Median and associated 95% CI, 25-75 percentiles, and minimum and maximum values will be presented. The number and percentage of patients whose symptoms resolved, and patients censored will be presented.

The differences in time to sustained clinical resolution between the treatment groups will be evaluated using a 2-sided log-rank test, stratified for baseline symptom severity (presence vs absence of moderate or severe symptoms) and by age ( $\leq 65$  years vs  $> 65$  years). The combined two highest treatment groups will be compared to placebo in addition to the comparison of individual doses.

#### **8.4.2. Analysis of Secondary Efficacy Endpoints**

##### **8.4.2.1. Time to Complete Clinical Resolution**

Time to complete clinical resolution will be analyzed using the same model as time to sustained clinical resolution, but with all symptoms required to have resolved to a score of 0 rather than 1.

#### ***8.4.2.2. Change from Baseline in COVID-19 Symptom Severity Score***

COVID-19 total symptom severity score will be summarized by treatment group using descriptive statistics (N, mean, median, standard deviation, minimum, and maximum) for each visit as well as for changes from baseline (N, mean, standard error, CI). A Mixed-Effect Model Repeated Measure (MMRM) will be performed to analyze the average difference between treatment groups over 28 days and at the designated assessment days.

#### ***8.4.2.3. Scoring of WHO Clinical Outcome Scale (9-point Scale)***

The number and percentage of patients for each WHO clinical outcome score will be summarized. An ordinal logistic regression analysis for the specified time points will be presented as odds ratio, with associated 95% CI and p-value.

#### ***8.4.2.4. Rate of Hospitalization Through Day 28***

The analysis of this endpoint will be performed on the ITT population. The number and percentage of patients who were hospitalized and reason for hospitalized will be presented. The percentage of patients who were hospitalized will be compared using a logistic regression analysis for specified time points. The results will be presented as odds ratios, with associated 95% CIs and p-value.

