#### **4.4.5. Follow-up of Patients Prematurely Discontinued from the Study Treatment Regimen or Withdrawn from Study**

Due to continued scientific importance of patient data even if study treatment is discontinued early, patients who withdraw from the study will be asked to complete all subsequent study procedures (Follow-up/EOS), as described in the Schedule of Assessments ([Appendix 4](#)). Patients who are no longer hospitalized may complete their assessments by telephone or via telemedicine or other means of remote communication.

All SAEs that are ongoing at the time of discontinuation, or that develop prior to the final Follow-up/EOS, will be followed until resolution or stabilization, or up to 28 days ( $\pm 2$  days) following the last dose of study treatment, by Covance Patient Safety Services group.

Steps will be taken by the sites to ascertain vital status in all randomized patients (e.g., with a vital records search) up to Day  $28 \pm 2$ .

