## **8.8. Handling of Missing Data**

### **8.8.1. Imputation**

Severity Symptom Score: Missing values on severity symptom score will not be imputed. Where a patient has died, their status will not be considered missing, but will be imputed with maximum severity score at each timepoint.

Clinical Outcome Scale: Missing values on clinical outcome scale will not be imputed. Where a patient has died, their status will not be considered missing, but will be imputed with maximum clinical outcome scale at each timepoint.

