#### 4.2 Secondary Efficacy Endpoints

The key secondary efficacy endpoints are:

- Change from baseline in log10 viral load, as measured using saliva and as measured using nasal swab. Changes will be calculated as value at follow-up visits – value at baseline.
- Time to sustained clinical resolution of symptoms.

Sustained clinical resolution is defined as occurring when no key COVID-19 related symptom has a score higher than 1 over a 72-hour period (as documented using an electronic patient-reported outcome [ePRO] instrument or in the eCRF), except for sense of smell and taste (items 13 and 14) where the score should be 0 over a 72-hour period. The time to resolution will be taken as the time from randomization until the first day of the last 72-hour period where the patient meets the definition of resolution within 28 days. Patients who do not meet the definition of resolution 28 days after randomization will be considered not resolved.

Refer to the algorithm in Appendix 1 for the derivation of this endpoint.

Other secondary efficacy endpoints are:

- Time to viral clearance based on PCR test for SARS-CoV-2, as measured using saliva and as measured using nasal swab
- Time to complete clinical resolution of symptoms (excluding cough, sense of smell and taste)

Clinical resolution is defined in the same way as the primary endpoint, but considering that all symptoms (excluding cough, sense of smell and taste) must resolve to a score of 0 for 72 hours.

- Time to complete clinical resolution of symptoms

Clinical resolution is defined as occurring when all key COVID-19 related symptom must resolve to a score of 0 for 72 hours.

The derivation of this endpoint follows similar steps as the algorithm presented in Appendix 1.

- Change from baseline in COVID-19 total symptom score

Total symptom score is defined as the sum [range 0-42] of the scores of all 14 common COVID-19 symptoms.

- Score on the WHO Clinical Outcome Scale (9-point scale) [as collected on eCRF Form “WHO COVID-19 Clinical Improvement Score”]
- Rate of hospitalization [hospitalization will be identified in the eCRF Form “Adverse Event” if adverse event is serious and serious category is Hospitalization or prolonged hospitalization]
- Rate of progression to oxygen therapy [progression to oxygen therapy will be identified in the eCRF Form “Adverse Event” if event requires supplemental oxygenation or mechanical ventilation or extracorporeal membrane oxygenation]

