- Duration of hospitalization [duration will be identified in the eCRF Form “Adverse Event” as the difference between date of discharge and date of admission]
- Mortality rate [death will be identified in the eCRF Form “Adverse Event” if outcome of adverse event is fatal]

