#### **6.4.3.6 Rate of Hospitalization Through Day 28**

The number and percentage of patients who were hospitalized will be presented. The percentage of patients who were hospitalized will be compared using a binary logistic regression analysis. The model will include only the treatment group. Contrasts under this model will allow for the comparisons across treatment groups. The results will be presented as odds ratios, with associated 80% CIs and p-value. The period will cover from the time of randomization to 28 days after, any hospitalization for which date of hospitalization > date of randomization + 28 would be excluded.

A listing with details on hospitalizations will be incorporated as part of the AE listing (Section 7, Listing 9).

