#### **6.4.3.7 Rate of Progression to Oxygen Therapy Through Day 28**

The analysis of this endpoint will be performed on the ITT population. The number and percentage of patients who progress to oxygen therapy and type of oxygen therapy will be presented. The percentage of patients who had progressed to oxygen therapy will be compared using a binary logistic regression analysis. The model will include only the treatment group. Contrasts under this model will allow for the comparisons across treatment groups. The results will be presented as odds ratios, with associated 80% CIs and p-value. The period will cover from the time of randomization to 28 days after, any progression to oxygen therapy for which date of progression > date of randomization + 28 would be excluded.

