#### 6.4.3.9 Mortality Rate

The analysis of this endpoint will be performed on the ITT population. The number and percentage of patients who died will be presented. The percentage of patients who died will be compared using a binary logistic regression. The model will include only the treatment group. Contrasts under this model will allow for the comparisons across treatment groups. The results will be presented as odds ratios, with associated 80% CIs and p-values. The period will cover from the time of randomization to 28 days after, any death for which date of death > date of randomization + 28 would be excluded.

A listing with details on deaths will be provided (Section 7, Listing 10).

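### No rule covers unknown Day 28 status for hospitalization, oxygen therapy and death, and a death without admission or oxygen is a non-event on the first two

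*Protocol*

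**What the plan says.** **Analysis.** Protocol 8.4.2.4 says of hospitalization: "The percentage of patients who were hospitalized will be compared using a logistic regression analysis for specified time points". Sections 8.4.2.5 (oxygen therapy) and 8.4.2.7 (mortality) use the same method. SAP section 1 gives the SAP precedence where the two differ. SAP 6.4.3.6 reads: "The percentage of patients who were hospitalized will be compared using a binary logistic regression analysis". SAP 6.4.3.7 reads: "The percentage of patients who had progressed to oxygen therapy will be compared using a binary logistic regression analysis", and SAP 6.4.3.9: "The percentage of patients who died will be compared using a binary logistic regression". Each model contains treatment group only, on the ITT population. The one timing rule drops events dated more than 28 days after randomization.

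**Derivation.** SAP 4.2 defines each event by a form entry: "hospitalization will be identified in the eCRF Form “Adverse Event” if adverse event is serious and serious category is Hospitalization or prolonged hospitalization". Oxygen therapy comes from the same form, and death is identified there "if outcome of adverse event is fatal".

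**Missing data.** Protocol 8.8 and SAP 6.2.2 deal with symptom scores, the WHO scale and viral data. They do not mention these three endpoints. For symptom scores, Protocol 8.8.1 says: "Where a patient has died, their status will not be considered missing, but will be imputed with maximum severity score at each timepoint". The WHO scale also gives death the worst score.

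**Follow-up.** The Protocol Synopsis provides for calls to Day 28±2 for patients who withdraw from the study; SAP 2.1 says this of patients who withdraw from study treatment. Protocol 4.4.5 adds: "Steps will be taken by the sites to ascertain vital status in all randomized patients".

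**The concern.** When an event exists only if a form entry shows it, and the denominator is the whole ITT population, having no entry amounts to having no event unless the plan says otherwise. A patient lost on Day 4 would then be scored like one seen well on Day 28. The plan expects incomplete follow-up: SAP Appendix 1 classes anyone without a Day 28 symptom assessment as not resolved, and SAP 6.4.4 adds a sensitivity analysis for them. The same patient is thus unfavourable on the primary endpoint and, by default, favourable on hospitalization, with no sensitivity analysis there.

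A death without admission or oxygen needs no inference: under SAP 4.2 it is a non-event on both endpoints. SAP 6.4.1 mentions a competing-risk model only for the symptom-resolution curve, although its methods are carried over to other time-to-event endpoints and not to these three.

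These are the trial's disease-progression outcomes. Rates could be understated, and unequal loss could look like a drug effect or hide one.

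**Working it through.** **Inputs.** Allocation is 52 per arm, so the two highest doses against placebo is 104 v 52. The documents give no expected rate of hospitalization, oxygen therapy, death or loss. The 20% in Protocol 8.1 is an allowance for non-resolution, and the 127 events belong to the primary endpoint, so there is no plan figure to reproduce here. The rest is assumed: true Day 28 risk r of 2-10%, the same in both groups; loss d of 5-20%; and a share q, from half to all, of a lost patient's risk unseen.

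**Expected events.** Placebo: 52 × 0.02 = 1.0 to 52 × 0.10 = 5.2. Two highest doses: 104 × 0.02 = 2.1 to 104 × 0.10 = 10.4.

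**Counting unseen patients as event-free.** Observed risk = r(1 − d × q). For r = 5% and a true odds ratio of 1:

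| Loss, placebo / active | q | Observed placebo | Observed active | Odds ratio |
|---|---|---|---|---|
| 10% / 10% | 1 | 4.50% | 4.50% | 1.00 |
| 5% / 15% | 0.5 | 4.88% | 4.63% | 0.946 |
| 5% / 15% | 1 | 4.75% | 4.25% | 0.890 |
| 15% / 5% | 0.5 | 4.63% | 4.88% | 1.057 |
| 15% / 5% | 1 | 4.25% | 4.75% | 1.124 |

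Over r = 2-10%, the 10-point imbalance gives 0.885-0.948 in one direction and 1.055-1.130 in the other. Equal loss of 5-20% with q = 1 lowers an observed 5% rate to between 4.75% and 4.0% and leaves the odds ratio at 1.

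**Against sampling error.** At r = 5% the expected counts are 5.2 of 104 and 2.6 of 52. The standard error of the log odds ratio is √(1/5.2 + 1/98.8 + 1/2.6 + 1/49.4) = √0.607 = 0.78. The shift ln(0.890) = −0.117 is 15% of that.

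**Fragility (illustration).** Suppose 3/104 v 3/52 are recorded as hospitalized, with 10 active and 5 placebo patients of unknown status.

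- Unknown counted as event-free: (3/101)/(3/49) = 0.49.
- All 10 unknown active patients had events: (13/91)/(3/49) = 2.33.
- All 5 unknown placebo patients had events: (3/101)/(8/44) = 0.16.
- Only 3 of the 10 unknown active patients had events: (6/98)/(3/49) = 1.00. With 4: (7/97)/(3/49) = 1.18.

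**Death without admission (same illustration).** Counting one such placebo death as an event moves 0.49 to (3/101)/(4/48) = 0.36. Counting two such active deaths instead moves it to (5/99)/(3/49) = 0.82. One patient is 1/52 = 1.9 percentage points of an arm.

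**The case against.** - **Nothing says a dropout is event-free.** A reader might infer that the plan scores them so, but that is an inference from silence. Setting unknown status to missing also fits the text. What stands is that the two readings give different results and the SAP does not choose.
- **Follow-up continues after withdrawal.** Beyond the calls and the vital-status check, Protocol 4.4.5 asks withdrawn patients to complete later procedures, 7.2.1 draws on hospital records, and Appendix 4 confirms the care setting at visits and records dates of WHO-scale change. This should make unknown status uncommon. It does not help with patients who cannot be reached, whom Protocol 4.4.3 treats as lost.
- **Deaths would probably be captured.** A reader might infer that deaths found by the vital-status check are left out. No passage says so: death is a seriousness criterion, and such a death would probably be entered as a fatal adverse event. A sentence naming the check as a source, and a rule for unknown status, are still needed.
- **Death is handled elsewhere.** It has its own analysis, and the WHO-scale comparison ranks it worst. A rate of hospitalization that counts only hospitalizations is not an error, so a composite belongs beside it.
- **The bias need not favour the drug.** Protocol 1.3 reports dose-limiting gastrointestinal toxicity in monkeys, but also a low rate of discontinuation for adverse events in people at 300-900 mg. Stopping the drug is also not the same as loss to follow-up. Greater loss at high doses is possible, not shown.

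**Conclusion.** The concern holds as a gap in specification and a missed inexpensive analysis. The plan has no rule for unknown Day 28 status on three endpoints, and its default leans towards counting such patients as non-events. Death without admission or oxygen is a non-event on two of them by definition.

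The expected bias is small: none in the odds ratio with equal loss, and about 5-13% in either direction with a 10-point imbalance, a fraction of the sampling error. All of that rests on assumed rates. The stronger reason to act is fragility. With about 1-5 placebo events and 2-10 on the two highest doses, a few unknown patients can change the direction of the estimate, and SAP 6.2 and 6.2.3 test at a two-sided 0.20 without multiplicity adjustment.

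The documents do not support a reading that these analyses are biased towards dalcetrapib, or that deaths are missed. The endpoints are classed as other secondary, so the primary conclusion is unaffected.

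A related inconsistency could understate rates more directly. Protocol 7.2.1 says non-fatal serious worsening of COVID-19 will not be collected for the safety database, while SAP 4.2 reads hospitalization and oxygen therapy from the Adverse Event form. No time-to-event method recovers events that were never recorded.

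**What to change.** Keep the protocol-defined rates and add to the SAP:

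1. In 6.4.3.6 and 6.4.3.7, the Day 28 Kaplan-Meier risk of hospitalization or death, and of oxygen therapy or death, censored at last contact, with risk differences and confidence intervals.
2. The components beside each composite, as cumulative incidence with death as a competing event. Censoring at death would not be suitable for hospitalization or oxygen therapy alone.
3. In 6.2.2, a rule that a patient with no recorded event and last contact before Day 28 has unknown status and is not counted as event-free. Report the number per arm, with best/worst-case bounds. The bounds matter because Kaplan-Meier censoring assumes that loss is unrelated to outcome.
4. In 4.2 and 6.4.3.9, deaths taken from every source, naming the vital-status check of Protocol 4.4.5.
5. A reconciliation of Protocol 7.2.1 with SAP 4.2, stating where hospitalizations and oxygen therapy for worsening COVID-19 are recorded and which source feeds these endpoints.

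Items 1 to 4 use data the protocol already plans to collect. They cost SAP wording, a little programming and two added composites whose components must be shown. Item 5 needs the documents aligned and a check that the events are in the database.

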#### ***8.4.2.5. Rate of Progression to Oxygen Therapy Through Day 28***

The analysis of this endpoint will be performed on the ITT population. The number and percentage of patients who progress to oxygen therapy and type of oxygen therapy will be presented. The percentage of patients who had progressed to oxygen therapy will be compared using a logistic regression analysis for specified time points. The results will be presented as odds ratios, with associated 95% CIs and p-value.

#### ***8.4.2.6. Duration of Hospitalization***

The duration of hospitalization will be performed on the ITT population. Duration of hospitalization will be summarized by treatment group using descriptive statistics (N, mean, median, standard deviation, standard error, CI, minimum, and maximum). Linear regression will be performed to analyze the difference between treatment groups. The results will be presented as mean treatment difference with associated 95% CI and p-value.

#### ***8.4.2.7. Mortality Rate***

The analysis of this endpoint will be performed on the ITT population. The number and percentage of patients who died and reason for death will be presented. The percentage of patients who died will be compared using a logistic regression analysis for specified time points. The results will be presented as odds ratios, with associated 95% CIs and p-values.

#### **8.4.2.8. *Time to Viral Clearance Based on PCR Test for SARS-CoV-2***

The time to viral clearance based on PCR test for SARS-CoV-2 will be performed on the ITT population. Time to viral clearance will be summarized by treatment group using Kaplan-Meier methods. Median and associated 95% CI, 25-75 percentiles, and minimum and maximum values will be presented. The number and percentage of patients who do not show virus, show virus, and patients censored will be presented.

#### **8.4.2.9. *Change from Baseline in log10 Viral Load***

The change from baseline in log10 viral load will be assessed at specified time points by a MMRM. Patients who have achieved a level below the limit of detection will be included in the analysis at half the lower limit of detection. For this endpoint, Last Observation Carried Forward (LOCF) will be used to impute values for all patients. The treatment effect for the difference at each time point, and the average slope up to each time point for each treatment group will be presented along with a 95% CI.

### **8.5. Safety Analysis**

Safety variables include incidence of AEs (or TEAEs), laboratory test results, and vital signs. All safety analyses will be based on the Safety Population. No formal statistical analysis of the safety data will be performed.

Adverse events will be coded according to MedDRA, version 23.0 released 19 Apr 2020 (exclusively meant for COVID-19) or later.

The number and percentage of patients with TEAEs, SAEs, TEAEs related to study treatment, SAEs related to study treatment, TEAEs leading to treatment discontinuation, TEAEs leading to study discontinuation, and TEAEs leading to death will be summarized by SOC, preferred term (PT), and treatment group. In addition, the severity of TEAEs and relationship to study treatment will be summarized by SOC, PT, and treatment group.

The AE summary tables will include counts of patients. Therefore, if a patient experiences more than 1 episode of a particular AE, the patient will be counted only once for that event. If a patient has more than one AE that is coded to the same PT, the patient will be counted only once for that PT. Similarly, if a patient has more than 1 AE within a SOC, the patient will be counted only once in that SOC.

Test values and change from baseline will be summarized descriptively by treatment group for specific laboratory test results and vital signs. Where applicable, shift tabulations will be presented for specific laboratory test results by treatment group. Where applicable, number and frequency of clinically significant abnormal values for specific laboratory test results will be presented.

Pregnancy test results and patients with confirmed positive pregnancy test result will be listed.

